#### **7.0 Patient Disposition**

The following will be summarized by randomized treatment group as well as overall:

- number of subjects randomized,
- number of subjects included in key analysis populations (Full Analysis Set and Per Protocol Analysis Set for primary efficacy analysis, Safety Analysis Set for analysis prior to Week 12 treatment switching),
- number of subjects who completed Period 1 study participation,

- number of subjects who entered Period 2,
- number of subjects who completed overall study (Period 1 and Period 2) participation (not applicable for Period 1 reporting).

This summary will be repeated by site.

Premature discontinuation details will be further summarized separately for Period 1 and Period 2 as follows.

### **Period 1**

The number and percentage of subjects completed Period 1 and prematurely discontinued in Period 1 will be summarized by randomized treatment group, separately by study drug and study participation completion/discontinuation, with the primary reason for discontinuation collected from CRF by the following categories:

- Adverse event (AE)
- Withdrew consent
- Lost to follow-up
- Lack of efficacy
- Other.

Subjects may have more than one reason for discontinuing, but only the primary reason will be summarized.

In addition, the number and percentage of subjects enrolled in Period 2 will also be summarized by randomized treatment group.

### **Period 2**

Period 2 patient dispositions and reason for discontinuation will be summarized for overall and by treatment regimen when entering Period 2 defined as follows:

1. Upadacitinib 15 mg QD

## 2. Upadacitinib 30 mg QD

Among the subjects who entered Period 2 participation (regardless of whether subject prematurely discontinued study drug in Period 1), the number and percentage of subjects completed and prematurely discontinued study participation in Period 2 will be summarized. Among the subjects who entered Period 2 upon completion of study drug in Period 1, the number and percentage of subjects completed and prematurely discontinued study drug in Period 2 will be summarized.

For subjects who prematurely discontinued study drug or study participation, the primary reason as well as all reasons for discontinuation will be summarized by the following categories (as collected in CRF):

- Adverse event (AE)
- Withdrew consent
- Lost to follow-up
- Lack of efficacy
- Other

### **Summary of Dose Switch from Upadacitinib 30 mg QD to 15 mg QD**

Starting with Amendment 4, all subjects will receive open-label upadacitinib 15 mg QD, including those currently on upadacitinib 30 mg QD. The visit at which dose switch occurs could be different for each subject. For subjects on upadacitinib 30 mg QD in Period 2, the number and percentage of subjects switching to upadacitinib 15 mg QD at each visit will be summarized.

## **8.0 Study Drug Exposure and Compliance**

### **8.1 Study Drug Exposure**

The duration of exposure to study drug will be summarized for the safety analysis set by the following groups.

1. Placebo

2. Upadacitinib 15 mg QD

This includes Upadacitinib 15 mg QD exposure from subjects starting on Upadacitinib 15 mg QD and subjects switching from placebo to Upadacitinib 15 mg QD.

3. Upadacitinib 30 mg QD

4. This includes Upadacitinib 30 mg QD exposure from subjects starting on Upadacitinib 30 mg QD and subjects switching from placebo to Upadacitinib 30 mg QD. Exposure is censored at time of dose switch from Upadacitinib 30 mg QD to Upadacitinib 15 mg QD. Upadacitinib 15 mg QD switched from Upadacitinib 30 mg QD

This includes Upadacitinib 15 mg QD exposure from subjects who switched dose from Upadacitinib 30 mg QD to Upadacitinib 15 mg QD.

Starting with Amendment 4, all subjects will receive open-label upadacitinib 15 mg QD, including those currently on upadacitinib 30 mg QD. Exposure to upadacitinib 30 mg QD (Group 3) will be censored prior to the day subject received the first dose of upadacitinib 15 mg QD, and subsequent exposure to upadacitinib 15 mg QD will be summarized under a separate group (Group 4).

The duration of exposure to study drug will be summarized for each group as specified above, with the number of subjects, mean, standard deviation, median, minimum and maximum values. In addition, the number and percentage of subjects exposed to study drug will be summarized for the following cumulative duration intervals.

- $\geq 2$  weeks
- $\geq 1$  month
- $\geq 3$  months
- $\geq 6$  months

- $\geq 9$  months
- $\geq 12$  months
- $\geq 18$  months
- $\geq 2$  years
- $\geq 2.5$  years
- $\geq 3$  years
- $\geq 4$  years

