## **5.6 Discussion and Justification of Study Design**

### **5.6.1 Discussion of Study Design and Choice of Control Groups**

This study includes two periods:

Period 1 is a 24-week, randomized, double-blind, placebo-controlled period to compare safety and efficacy of upadacitinib versus placebo in subjects with moderately to severely active RA who have an inadequate response to or intolerance to bDMARD therapy and who are on a stable dose of csDMARDs. Period 1 is designed to test superiority of upadacitinib versus placebo for achieving the primary endpoint (ACR20 for US/FDA regulatory purposes or LDA for EU/EMA regulatory purposes) at Week 12, and other secondary efficacy parameters, all on a stable background csDMARD therapy.

The purpose of Period 2 is to evaluate the long-term safety, tolerability, and efficacy of upadacitinib 30 mg QD and 15 mg QD in a blinded fashion in subjects with RA who have completed Period 1. Subjects will continue to receive upadacitinib 15 mg QD or 30 mg QD per original randomization assignment in a blinded manner. Dose reduction or escalation of upadacitinib during Period 2 is not permitted to allow unbiased assessments of long-term safety and efficacy of upadacitinib 30 mg QD versus 15 mg QD.

Starting with Amendment 4, all subjects will receive open-label upadacitinib 15 mg QD, including those currently on upadacitinib 30 mg QD.

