### 10.2.2 Analysis of Long-Term Adverse Event Rates

Long-term adverse event rates will be analyzed using event rates adjusted by cumulative exposure and will be based on the actual treatment received at the time of AE occurrence. Starting with Amendment 4, all subjects will receive open-label upadacitinib 15 mg QD, including those currently on upadacitinib 30 mg QD. For subjects who previously received upadacitinib 30 mg QD, adverse events and exposure to upadacitinib 30 mg QD will be censored at the time of dose switch; subsequent adverse events and exposure

starting the day of first dose of upadacitinib 15 mg QD will be summarized under a separate group. The detailed treatment groups, including the handling of dose switch, are described in Section 8.1.

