#### **10.2.2.1 Overview of Adverse Events Rates per 100 Patient-Years of Study Drug Exposure**

An overview of AEs per 100 patient-years of study exposure will be presented by treatment group and overall for the following AE categories.

- All TEAEs
- Treatment-emergent serious adverse events (SAEs)
- Treatment-emergent severe adverse events
- TEAEs reasonably possibly related to study drug
- TEAEs of special interest
- TEAEs leading to discontinuation of study drug
- TEAE leading to death

For this calculation, 1 year will be considered to be 365.25 days. For each treatment group, the numerator of the overall rate will be the total number of TEAEs reported for the event; that is, a subject can contribute more than one event to the numerator. For each treatment group, the denominator of the rates will be the total number of days exposed to study drug summed across all treated subjects divided by 365.25. Please refer to Section 6.0 for the calculation of study drug exposure. The AE rate per 100 patient-years of exposure will be calculated as  $([\text{numerator}/\text{denominator}]) * 100$ . The number of AEs reported (numerator), the total number of years of study drug exposure (denominator), and the AE rate per 100 patient-years will be presented for each treatment group and overall.

In the AE overview summary, any event with an unknown severity will be considered as severe and any AE with an unknown relationship will be considered as having "reasonable possibility" of being related to study drug.

Additional AEs may be considered for tabulation/summary based on recommendations from Clinical and Safety as deemed appropriate.

For TEAEs of special interest, the point estimate and 95% CI (using normal approximation) will be provided for the treatment difference in AE rate per 100 patient-years between each Upadacitinib dose group and the combined placebo group.

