### **4.0 Safety Analysis**

In listings of adverse events and deaths, a flag indicating whether the event or death was related to COVID-19 infection will be presented. A listing of COVID-19 related adverse events may be provided.

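### Long-term 30 mg safety rates stop at the Amendment 4 dose switch while 15 mg rates run on to Week 260, so the side-by-side rates are not concurrent

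*SAP*

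**What the plan says.** SAP 8.1 defines four exposure groups: placebo, 15 mg, 30 mg, and 15 mg after a switch from 30 mg.

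- **15 mg (Group 2):** "This includes Upadacitinib 15 mg QD exposure from subjects starting on Upadacitinib 15 mg QD and subjects switching from placebo to Upadacitinib 15 mg QD". No end point at Amendment 4 is given.
- **30 mg (Group 3):** "Exposure to upadacitinib 30 mg QD (Group 3) will be censored prior to the day subject received the first dose of upadacitinib 15 mg QD".
- **Switched (Group 4):** "This includes Upadacitinib 15 mg QD exposure from subjects who switched dose from Upadacitinib 30 mg QD to Upadacitinib 15 mg QD".

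SAP 10.2.2 carries this into the event counts: "adverse events and exposure to upadacitinib 30 mg QD will be censored at the time of dose switch". It then refers back: "The detailed treatment groups, including the handling of dose switch, are described in Section 8.1". Rates are events per 100 patient-years pooled over all exposure in a group, and "a subject can contribute more than one event to the numerator" (SAP 10.2.2.1). The only long-term between-group estimate is each dose against combined placebo, for events of special interest. SAP 10.3.3.2, 10.3.3.3 and 10.4.3 reuse the same groups for potentially significant laboratory values, liver elevations and vital signs, reported as numbers and percentages of subjects.

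On COVID-19, SAP Appendix B section 4.0 adds to the listings only: "a flag indicating whether the event or death was related to COVID-19 infection will be presented". A listing of COVID-19 events may also be produced.

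Protocol 5.6.1 rules out changes of dose in Period 2 "to allow unbiased assessments of long-term safety and efficacy of upadacitinib 30 mg QD versus 15 mg QD". The same section then records that Amendment 4 moves everyone to open-label 15 mg.

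**The concern.** Up to the switch, the two doses are randomised, concurrent and blinded at site and subject level. After it, Group 2 keeps accruing and Group 3 does not. The added 15 mg time comes later in the calendar (all subjects were in Period 2 during the pandemic, per SAP Appendix B), later on drug, and open label (Protocol 5.5.5.1). An event whose reported rate changes with any of these will show a gap between the 15 mg and 30 mg columns even if dose has no effect.

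Nothing else in the SAP restores concurrency. I found no long-term event analysis by calendar period or time on drug, and no rate that excludes COVID-19 events. Protocol 6.1.4 has COVID-19 infections recorded as adverse events, and as serious ones when they qualify. SAP Table 8 takes serious infections as the serious subset of an infections query, with no COVID-19 exclusion stated.

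The percentage summaries have a further problem. Without exposure adjustment, longer 15 mg follow-up raises the 15 mg percentage even when rates are constant over time.

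**Working it through.** The documents state no long-term patient-years, event rates or power, so there is no figure of the plan's own to reproduce.

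**1. Where subjects stood at Amendment 4.** The original protocol is dated 21 January 2016 and Amendment 4 is dated 13 December 2019 (Protocol 1.1): 203 weeks. SAP Appendix B says Period 1 reporting was completed in 2017. A last Week 24 visit on 31 December 2017 would put the last randomisation at 16 July 2017, 126 weeks before Amendment 4. Subjects were thus at roughly Week 126 to 203 on that date. The lower figure is generous, since visit, database lock and reporting cannot share a day. Implementation then adds lag: approvals come first (Protocol 9.1), Period 2 visits are mostly 12 weeks apart, and the switch visit varies by subject (SAP 7.0).

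**2. Assumptions.** Switch at study Week 150 to 220, central 182. Discontinuation 0 to 0.20 per year at a constant rate, central 0.10. From the 2:2:1:1 allocation, 225 subjects per dose: 150 from Day 1 and 75 from Week 12.

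**3. Patient-years to week w**, with discontinuation rate d and 52.18 weeks per year:

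PY(w) = 225 × (1 − exp(−d·w/52.18))/d − 75 × (1 − exp(−d·12/52.18))/d

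Central case:
- 15 mg to Week 260: 882.9 − 17.1 = 866
- 30 mg to Week 182: 662.6 − 17.1 = 645 (rounded down from 645.5)
- 15 mg after the switch: 220, so f = 220/866 = 0.25

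Over the grid, f runs from 0.10 (Week 220, 0.20 per year) to 0.43 (Week 150, no discontinuation).

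**4. Apparent ratio under equal dose risk.** If the later event rate is c times the earlier one, the 15/30 rate ratio is 1 − f + f·c.

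| c | Central case (f = 0.255) |
|---|---|
| 0.5 | 0.87 |
| 0.7 | 0.92 |
| 1 | 1.00 |
| 1.5 | 1.13 |
| 2 | 1.25 |
| 3 | 1.51 |

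Over the grid, with c from 0.5 to 3, the range is 0.79 to 1.86.

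**5. Against sampling error (central case, assumed base rates).**
- Base 4 per 100 patient-years, c = 2: 5.0 against 4.0, difference 1.0 (95% CI −1.1 to 3.2).
- Base 250 per 100 patient-years (all events), c = 1.5: 282 against 250, difference 32 (95% CI 15 to 48). This Poisson interval ignores repeated events within subjects, so it is too narrow.

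**6. Unadjusted percentages.** With a constant first-event rate h = 0.03 per year on both doses and d = 0.10, the proportion ever affected by time T is h/(h + d) × (1 − exp(−(h + d)T)). For simplicity all subjects are counted from Day 1.
- 15 mg, T = 260/52.18 = 4.98 years: 0.231 × 0.477 = 11.0%
- 30 mg, T = 182/52.18 = 3.49 years: 0.231 × 0.365 = 8.4%

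**7. With a matching cut.** If 15 mg also stops at the transition, f = 0 and the ratio is 1.00 for every c, with about 645 patient-years per dose in the central case.

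**The case against.** The strongest reply is that the SAP plans no long-term 15 versus 30 mg difference, interval or test, and that the words quoted from Protocol 5.6.1 justify a design rule that Amendment 4 later overtook. That stands as far as it goes: a reader might infer that a biased formal dose comparison is specified, and it is not. But the rates appear side by side, and the two planned differences share one placebo comparator, so the gap between them equals the 15 minus 30 mg difference.

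Second, the planned grouping is sensible. Stopping 30 mg at the switch and isolating Group 4 avoids charging 30 mg with events on 15 mg. I agree; only the matching cut is missing. About 75% of 15 mg patient-years (645 of 866, central case) are concurrent as planned.

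Third, unequal follow-up will be visible from the exposure intervals (SAP 8.1) and the switch-by-visit table (SAP 7.0), and additional event tabulations are allowed. Visibility does not remove the distortion, and an optional table is not a commitment.

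Fourth, for uncommon events the artefact may be smaller than sampling error, as step 5 shows. That also stands, though it is less true of frequent events.

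**Conclusion.** The asymmetry is explicit in SAP 8.1 and 10.2.2, and nothing else in the plan offsets it. About 10% to 43% of 15 mg patient-years, centrally about 25%, have no concurrent 30 mg counterpart. This rests on assumed switch weeks and discontinuation, because enrolment and switch dates are not given. The effect on a rate depends on c, which is unknown.

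Four stronger readings go beyond the documents:

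- **That 15 mg rates are necessarily inflated.** COVID-19 could raise infection rates, while fewer contacts or loss of susceptible subjects could lower rates. With constant rates there is no distortion of the rates.
- **That the tail is 22% to 52%.** Those shares, (260 − 203)/260 and (260 − 126)/260, describe the earliest and latest possible single subject, with no discontinuation and no implementation lag. They are not group values.
- **That 30 mg has no pandemic or late exposure.** Switch visits vary and may extend into 2020, and the earliest 30 mg subjects could have been near the end of year 4 at Amendment 4.
- **That completed results are affected.** SAP 11.1 limits version 3.0 to future long-term reporting. The primary analysis and Period 1 reporting are untouched.

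This is a gap in a descriptive safety analysis that is cheap to close and worth closing.

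**What to change.** Keep the planned groups in SAP 8.1, including the all-exposure 15 mg column. Add a sensitivity set to SAP 10.2.2.1 and 10.2.2.3, and to the summaries in 10.3.3.2, 10.3.3.3 and 10.4.3, in which Group 2 is split at each subject's first open-label 15 mg dispensing under Amendment 4. Subjects who stopped drug earlier contribute all their time to the first part. Present:

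1. 15 mg and 30 mg, both up to that point. This is the concurrent dose comparison.
2. Continuing 15 mg and 15 mg switched from 30 mg, after that point. Label it as a comparison among subjects still on drug, with possible carry-over from 30 mg; it does not replace a 30 mg comparator.
3. Serious-infection rates with and without COVID-19 events.

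The cost is SAP wording and one extra set of tables. Dispensing dates are held in the IRT (Protocol 5.5.7), and COVID-19 events have their own supplemental forms (Protocol 6.1.4), so no new data are needed. The concurrent table uses about 25% fewer 15 mg patient-years in the central case (about 645 instead of 866); no other table loses exposure.

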## **8.2 Compliance**

Study drug compliance will be summarized for each treatment group for Period 1. The compliance is defined as the number of tablets taken (i.e., the difference between the number of tablets dispensed and the number of tablets returned) during the subject's participation in Period 1 divided by the number of days that the subject was in the Treatment Phase of Period 1.

## **9.0 Efficacy Analysis**

### **9.1 General Considerations**

There are two sets of planned efficacy analysis: efficacy analysis by Week 12 and long-term efficacy analysis. All efficacy analyses will be carried out using the FAS population.

#### **9.1.1 Efficacy Analysis at Different Phases of the Study**

##### **Efficacy Analysis by Week 12**

Standard efficacy analysis by randomized treatment groups (Upadacitinib 15 mg QD, Upadacitinib 30 mg QD and the combined placebo groups) will be performed on efficacy data up to Week 12. No protocol-defined treatment switching will occur prior to the time point. Formal statistical inference will be generated, and results from this set of analysis will be used as the key efficacy findings of this study.

### **Long-Term Efficacy Analysis**

Long-term efficacy analysis will be performed on As Observed data (defined in Section 9.1.2) by randomized treatment group sequence as described below:

1. Placebo → Upadacitinib 15 mg QD
2. Placebo → Upadacitinib 30 mg QD
3. Upadacitinib 15 mg QD
4. Upadacitinib 30 mg QD

There will be no statistical testing; only descriptive statistics and confidence intervals will be provided.

Starting with Amendment 4, all subjects will receive open-label upadacitinib 15 mg QD, including those currently on upadacitinib 30 mg QD. For long-term efficacy analysis, subjects will continue to be summarized under the treatment sequences as described above, regardless of dose switch – i.e., for treatment sequences 2 and 4, data collected after dose switch will continue to be summarized under the same treatment sequences. The visit at which dose switch occurs could be different for each subject. The first and last visits at which dose switch occurs will be noted in the summary.

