**Discontinuation of Study Drug and Continuation of Study Participation Period 1 and Period 2)**

Subjects may discontinue study drug treatment but may choose to continue to participate in the study (refer to Section 5.4.1 for additional details). Subjects who prematurely discontinue study drug should complete a Premature Discontinuation visit (PD visit) as soon as possible, preferably within 2 weeks, and preferably prior to initiation of another therapy. To minimize missing data for efficacy and safety assessments, subjects who prematurely discontinue study drug treatment should continue to be followed for all regularly scheduled visits as outlined in the Activity Schedule ([Appendix D](#) and [Appendix F](#)), unless subjects have decided to discontinue study participation entirely (withdrawal of informed consent). Subjects should be advised on the continued scientific importance of their data even if they discontinue treatment with study drug early. Following discontinuation of study drug, the subject should be treated in accordance with the investigator's best clinical judgment irrespective of whether the subject decides to continue participation in the study. As the subject has discontinued study drug, all rescue and efficacy driven discontinuation criteria no longer apply (e.g., CDAI calculation at Week 24, 20% TJC/SJC calculation for PD). If at any point a subject no longer wants to provide assessments (withdrawal of informed consent) following discontinuation of study drug, a second (PD visit) is not required.

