### **As Observed (AO)**

The AO analysis will not impute values for missing evaluations. Regardless of treatment switching or premature discontinuation of study drug, all observed data will be used in the analysis. The AO analysis will be applied to long-term efficacy analysis.

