### **MMRM and Generalized Linear Mixed Model (GLMM) for Long-Term Analysis**

The repeated measure analysis will be conducted using mixed model including As Observed measurements at all visits. MMRM will be used for continuous endpoints and GLMM will be used for binary endpoints. The mixed models will include the categorical fixed effects of treatment, visit and treatment-by-visit interaction, and main stratification factor prior bDMARD use. For the MMRM analysis of change from baseline in continuous endpoints, the baseline measurement will be included as a continuous fixed covariate. The categorical fixed effect of subject's discontinuation status may also be

included in the model as appropriate. Unstructured, Toeplitz, compound symmetry, or other covariance structures may be considered.

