### 9.3 Long-Term Efficacy Analysis

Assessments to evaluate long-term efficacy will be analyzed for the following measures at Week 1, 2, 4, 8, 12, 24, 36, 48, every 12 weeks through Week 240, and at Week 260.

- ACR20/50/70 response rates;
- Change from baseline in individual ACR components;
- Change from baseline in DAS28 (CRP);
- Change from baseline in DAS28 (ESR);
- Change from baseline in CDAI;
- Change from baseline in SDAI;
- Change from baseline in morning stiffness (severity and duration);
- Proportion of subjects achieving LDA and proportion of subjects achieving CR based on DAS28 (CRP), DAS28 (ESR), SDAI, and CDAI criteria;
- Proportion of subjects achieving MCID in change from baseline in HAQ-DI (defined as change from baseline in HAQ-DI  $\leq -0.3$ );

- ACR/EULAR Boolean remission;
- Proportion of subjects with no concomitant corticosteroid use (among subjects with corticosteroid use at baseline).

Assessments to evaluate long-term efficacy will be analyzed for the following measures at Week 4, 12, 24, 48:

- Change from baseline in EQ-5D-5L;
- Change from baseline in ISI (sleep);
- Change from baseline in SF-36.

Analyses will be based on As Observed (AO) data. Descriptive statistics will be provided for each randomized treatment group sequence as defined in Section 9.1.1. These include the number of observations, mean, standard deviation, and 95% CI for continuous endpoints; and frequencies and percentages with 95% CI using normal approximation for binary endpoints. In addition, longitudinal analysis will be performed using MMRM or GLMM as described in Section 9.1.2 for all endpoints except proportion of subjects with no concomitant corticosteroid use. Point estimates and 95% CI from the model will be provided for each treatment group sequence. Plot for each randomized treatment group sequence over time will be provided.

For the purpose of Period 1 CSR, response rate and 95% CI using NRI for binary endpoints will be provided for each randomized treatment group sequence by visits up to Week 24. For continuous endpoints, the LS mean and 95% CI based on MMRM will be reported for each randomized treatment group sequence by visits up to Week 24.

Table 5 below provides the overview of the long-term efficacy analyses to be performed on different endpoints.

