**Table 5. Summary of Efficacy Variables and Corresponding Analyses for Long-Term Efficacy Analysis**

Efficacy Variables	Analysis Method
Binary Endpoints:	

 
• ACR20/50/70 response by visit
 
• LDA and CR based on DAS28(CRP), DAS28 (ESR), SDAI, and CDAI criteria by visit
 
• Proportion of subjects with change from baseline in HAQ-DI <math>\leq -0.3</math> and <math>\leq -0.22</math>, respectively
 
• Boolean remission
 
• Proportion of subjects with no concomitant corticosteroid use (among subjects with corticosteroid use at baseline)*
 
	
 
• Point estimate and 95% CI of the response rate for each randomized treatment group sequence
 
• Point estimate and 95% CI of the response rate using GLMM model for each randomized treatment group sequence (*endpoint excluded from this analysis)
 
• Plot for each randomized treatment group sequence over time for key endpoints#
 
• Imputation: AO
 
• Analysis Set: FAS
 

Continuous Endpoints:	

 
• Change from baseline in individual ACR components by visit
 
• Change from baseline in DAS28 (CRP) and DAS28(ESR) by visit
 
• Change from baseline in CDAI and SDAI by visit
 
• Change from baseline in morning stiffness (severity and duration) by visit
 
• Change from baseline in EQ-5D-5L by visit
 
• Change from baseline in ISI (sleep) by visit
 
• Change from baseline in SF-36 by visit
 
	
 
• Point estimate, and 95% CI of mean change from baseline together with SD for each randomized treatment group sequence
 
• Point estimate and 95% CI of change from baseline using MMRM model for each randomized treatment group sequence
 
• Plot for each randomized treatment group sequence over time for key endpoints#
 
• Imputation: AO Analysis Set: FAS
 

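### Once dose switching begins, the long-term efficacy outputs for the two 30 mg sequences mix 30 mg and post-switch 15 mg data under a 30 mg label, with no supplementary split

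*SAP*

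**What the plan says.** From Amendment 4 every subject moves to open-label 15 mg, including those on 30 mg, and the visit at which this happens can differ between subjects. Protocol 8.1 leaves the analytical handling of the change to the SAP.

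SAP 9.1.1 keeps subjects in their randomised sequence for long-term efficacy. For sequence 2 (placebo, then 30 mg) and sequence 4 (30 mg throughout), "data collected after dose switch will continue to be summarized under the same treatment sequences". The summary is to note the first and last visits at which switching occurs.

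The other efficacy provisions follow the same rule:

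- As Observed rule (SAP 9.1.2): "Regardless of treatment switching or premature discontinuation of study drug, all observed data will be used in the analysis".
- Long-term models (SAP 9.1.2): "The mixed models will include the categorical fixed effects of treatment, visit and treatment-by-visit interaction", plus prior bDMARD use, baseline for the MMRM, and optionally discontinuation status.
- Model output (SAP 9.3): "Point estimates and 95% CI from the model will be provided for each treatment group sequence".
- Figures (SAP Table 5): "Plot for each randomized treatment group sequence over time for key endpoints".
- Disposition (SAP 7.0): for subjects on 30 mg in Period 2, "the number and percentage of subjects switching to upadacitinib 15 mg QD at each visit will be summarized".
- COVID-19 appendix (SAP Appendix B, 3.0): the same longitudinal models are kept and no dose split is added.

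Exposure and safety are handled differently. SAP 8.1 and 10.2.2 end the 30 mg exposure and adverse-event period at the switch and report what follows in a separate group. SAP 10.1, 10.3.3.1 and 10.4.3 do the same for mean changes in laboratory values and vital signs, with post-switch values tabulated by visit since the switch.

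**The concern.** The Period 2 objective (Protocol 4.0, SAP 4.1) is long-term efficacy of 30 mg and of 15 mg. While switching is under way, a table row or curve labelled 30 mg averages subjects still on 30 mg with subjects already on 15 mg. Once all continuing subjects have switched, the same label describes 15 mg. The treatment term in the models is the sequence, so the model-based estimates carry the same mixture.

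The cost is interpretive. If response after the switch differs from response on 30 mg by *d*, a visit at which a share *p* has switched shows a shift of only about *p* × *d*. A change after dose reduction would therefore appear diluted and spread over several visits, and would be hard to tell from drift over time. Response after reduction in established patients is something these data could describe, but no planned output aligns efficacy to the switch.

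**Working it through.** The plan gives no figure on this point to reproduce. The check has two parts: a reading of every long-term efficacy output, and date arithmetic for scope.

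**Part 1: can any efficacy output separate the doses?**

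- Descriptive tables: by sequence, with no cut-off at the switch.
- MMRM and GLMM: sequence, visit, their interaction, prior bDMARD use, baseline (MMRM) and optional discontinuation status. None of these is current dose or time since switch.
- Plots: by sequence.
- First and last switch visits: they bracket the mixed window but give no estimate by dose inside it.
- Switch counts in SAP 7.0: numbers of subjects, not split efficacy results.

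So no output separates the doses within the mixed window.

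**Part 2: how many subjects and visits?**

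Subjects: sequence 2 has 75 planned and sequence 4 has 150. 75 + 150 = 225 of 450, or 50%.

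Inputs for timing:

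- Amendment 4: 13 December 2019 (Protocol 1.1).
- Start of accrual: 21 January 2016, the date of the original protocol. This is an assumption, since it is not an enrolment date.
- Latest baseline: SAP Appendix B says Period 1 reporting was completed in 2017, and SAP 4.4 places that analysis after all subjects had completed Week 24. 31 December 2017 minus 24 weeks = 16 July 2017. 1 March 2017 is taken as an assumed alternative.
- Roll-out lag after Amendment 4: 0, 26 or 52 weeks (assumed; Protocol 9.1 requires ethics approval of amendments).
- Accrual: uniform (assumed). Drop-out unrelated to enrolment date (assumed).
- Period 2 efficacy visits: Weeks 36 to 240 every 12 weeks (18 visits) plus Week 260 = 19.

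Study week at Amendment 4:

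- Earliest possible subject: 203.1.
- Latest subject: 145.3 (baseline 1 March 2017) or 125.7 (16 July 2017).

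Add the lag to get *low* and *high*. A subject switches at the first scheduled visit at or after roll-out, and data at that visit still count as pre-switch. Hence

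share switched at visit *v* = (previous visit − *low*) / (*high* − *low*), limited to 0–1.

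Examples with the 16 July 2017 baseline:

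- Lag 0, Week 132: (120 − 125.7) is negative, so 0%.
- Lag 0, Week 204: (192 − 125.7) / (203.1 − 125.7) = 66.3 / 77.4 = 86%.
- Lag 52, Week 240: (228 − 177.7) / 77.4 = 65%.

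| Lag (weeks) | Latest baseline | First switch visit | Mixed visits | Visits with any post-switch data | Wk 132 | Wk 204 | Wk 240 | Wk 260 |
|---|---|---|---|---|---|---|---|---|
| 0 | Mar 2017 | 156 | 4 | 8 | 0% | 81% | 100% | 100% |
| 0 | Jul 2017 | 132 | 6 | 10 | 0% | 86% | 100% | 100% |
| 26 | Mar 2017 | 180 | 5 | 6 | 0% | 36% | 98% | 100% |
| 26 | Jul 2017 | 156 | 7 | 8 | 0% | 52% | 99% | 100% |
| 52 | Mar 2017 | 204 | 4 | 4 | 0% | 0% | 53% | 74% |
| 52 | Jul 2017 | 180 | 6 | 6 | 0% | 18% | 65% | 80% |

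At lag 52 the Week 260 share stays below 100% because Protocol Appendix F schedules no dispensing at Week 260. Subjects past Week 240 at roll-out would never switch, and Week 260 would itself be mixed.

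For dilution only, with *d* assumed because the documents give no dose difference: at *p* = 50%, *d* = 5 points shows as 2.5 points and *d* = 10 points as 5 points.

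These are scenarios of switch status, not of drug actually taken. Under Protocol 5.1 "subjects who prematurely discontinue study drug treatment should continue to be followed for all regularly scheduled visits", so the As Observed data also contain off-drug assessments, which are not modelled here.

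**The case against.** The sponsor has a good answer on several counts. The rule is stated openly, was delegated to the SAP, and involves no long-term hypothesis test. The sequences are headed as randomised, so a label can be read as the assignment rather than the current dose. Efficacy by randomised group and safety by treatment received is the SAP's general convention, so the different safety handling is not in itself a contradiction. Visits up to the first switch still reflect the assigned dose, apart from off-drug assessments; under the scenarios above that covers at least the period through Week 132. The dose difference may be small: Protocol 5.6.4 matches 15 mg to a Phase 2 dose close to maximum efficacy and 30 mg to one on the plateau. A post-switch summary would have no concurrent 30 mg comparator and would overlap the COVID-19 period. All of this stands. It limits the point without removing it, because none of it yields a dose-specific efficacy summary inside the mixed window.

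Three stronger readings are tempting, and the documents do not support them:

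- *No output shows response after the reduction.* After the last switch visit, which is to be noted, on-drug data in sequences 2 and 4 are post-switch 15 mg, provided no continuing subject remains unswitched. In the table, visits with any post-switch data minus mixed visits leaves 4 fully post-switch visits at lag 0, 1 at lag 26 and none at lag 52. What is missing there is a correct label and alignment to the switch.
- *Mixing begins at the first switch visit.* Assessments at that visit precede the first 15 mg dose under the counting rule used here, so mixing begins at the next visit.
- *Baselines could run to April 2018.* Protocol 5.5.5.2 says that by September 2018 all subjects had reached the end of Period 1, which might suggest much earlier switch weeks. Completion of Period 1 reporting in 2017 excludes baselines that late, and the September 2018 statement is compatible with an earlier date.

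**Conclusion.** The point holds as a limit on interpretation of long-term efficacy. Between the first and last switch visits, no planned efficacy output distinguishes 30 mg from post-switch 15 mg in sequences 2 and 4. Afterwards the 30 mg label describes 15 mg, and response is nowhere aligned to the switch.

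Up to 225 of 450 planned subjects are in these sequences. Across the six scenarios the first switch visit falls at Week 132 to 204, 4 to 7 of 19 Period 2 visits are mixed, and 4 to 10 hold some post-switch data. The share switched is 0% at Week 132, 0–86% at Week 204, 53–100% at Week 240 and 74–100% at Week 260. Only the bound on the latest baseline is derived from the documents; accrual start and shape, the March 2017 alternative and the lags are assumptions. The effect on the reported estimates is unknown and may be small.

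A reader should not infer that the as-randomised display is wrong, or that the Week 12 results or their type I error control are touched. This is a worthwhile, inexpensive reporting improvement.

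**What to change.** Keep the as-randomised display as the main one, and amend SAP 9.1.1, 9.3 and Table 5 as follows:

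1. Relabel sequence 2 as *Placebo → 30 mg → 15 mg* and sequence 4 as *30 mg → 15 mg*.
2. Show the cumulative number switched at each visit in the efficacy tables and plots.
3. Add a supplementary descriptive efficacy summary that censors 30 mg data at the first 15 mg dose and reports later data separately by visits post switch, following SAP 10.1 for laboratory values and vital signs. State whether assessments after stopping study drug are included.
4. Pre-state a minimum number of subjects below which a 30 mg visit is shown as not estimable. Add a footnote that late 30 mg data come from the earliest enrolees and that post-switch data overlap the COVID-19 period.

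The cost is two labels, one count row and one set of descriptive tables. The switch date is already needed for exposure and safety. SAP 11.1 confines version 3.0 to future long-term reporting, so no completed analysis changes. The downsides to state are extra output, small numbers at late 30 mg visits, no concurrent 30 mg comparator, and confounding of post-switch data with calendar time and pandemic disruption.
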